#### 3.1.3 Pharmacokinetic Objectives

The PK objectives are to determine the concentration of V565 in serum and urine.

#### 3.1.4 Exploratory Objectives

The exploratory objectives are to:

- To assess the proportion of subjects achieving CRP or FCP levels within normal limits
- To assess changes in CDAI scores and CRP or FCP levels over time
- To determine changes in anti-V565 antibody titre

#### 3.1.5 Exploratory Endoscopy Substudy Objectives

• To investigate the effect of V565 on changes in endoscopic mucosal appearance, evaluated with an overall assessment and the Simple Endoscopic Score for Crohn's Disease (SES-CD), as determined by a central reader

# 4.0 INVESTIGATIONAL PLAN

### 4.1 Summary of Study Design

This study will be a multiple-site, double-blind, placebo-controlled, parallel-group proof-of-concept study in approximately 126 subjects with active CD. This study will include subjects who have a confirmed diagnosis of CD for at least three months and have CD involving the ileum and/or colon. Inclusion and exclusion criteria are described in detail in Section 4.4.

The duration of treatment will be 42 days (six weeks); each subject's participation in the study will be approximately 12 weeks. This includes a screening period of up to 28 days, a treatment period of 42 days and a follow-up period of 14 days after the last dose of study drug.

Subjects will be randomised into two treatment arms: either V565 or placebo using a 2:1 active:placebo ratio. Randomisation will be stratified to ensure treatment groups have similar rates of prior anti-TNF $\alpha$  therapy.

Subjects will receive three V565 185 mg capsules three times daily or matching placebo, for 42 days (six weeks). The total daily V565 dose is 1665 mg.

Subjects will be treated with study drug as an add-on to any permitted stable medications already being taken for CD. Permitted CD medications are described in Section 5.10.2. No alteration of background CD medication will be permitted for the duration of the study.

There are six study visits. Two screening visits to assess eligibility will occur during Days - 28 to Day -1; these are Visit 1 (start of screening), and Visit 2 (eligibility ileocolonoscopy). Additional study visits will occur on Day 1 (randomisation and initiation of treatment), Day 14 (Interim Visit), Day 42 (End of Treatment Visit), and Day 56 (Follow up Visit).

Collection of subject-reported variables of the CDAI will be via the diaries given to subjects at Visit 1. Prior to Visit 2, the subject-reported variables will be combined with the variables collected at the site on Visit 1 and the CDAI score will be calculated. In order to have an ileocolonoscopy, eligible subjects must have sufficient diary entries to calculate a CDAI score, a CDAI score  $\geq$ 220 to  $\leq$ 450 and a CRP  $\geq$ 5 mg/L (or if CRP is normal, FCP  $\geq$ 250 µg/g) prior to Visit 2.

A previous ileocolonoscopy conducted within 12 weeks before Visit 1 may be substituted for the Visit 2 ileocolonoscopy provided it is forwarded to the central reader and was performed in such a way as to enable evaluation by the central reader.

The Visit 2 ileocolonoscopy will be evaluated by a central reader for to assess the overall appearance of the mucosa for the presence of active disease and scored using the SES-CD.

Active disease must be confirmed by the central reader for the subject to proceed to Visit 3 and to be randomised on Day 1.

The efficacy of V565 will be evaluated throughout the study by assessing changes in CDAI scores and changes in inflammatory markers (CRP or FCP). Efficacy will also be evaluated with the PRO-2.

Exploratory efficacy measures include changes in CDAI scores, changes in CRP (or FCP) values over time,

This study

will also assess the immunogenicity of V565.

In an exploratory endoscopy substudy, subjects with more severe disease at the Visit 2 ileocolonoscopy (a SES-CD  $\geq$ 7, if ileum and colon are involved or  $\geq$ 4 if only the ileum is involved) will undergo a second ileocolonoscopy at the end of treatment (Day 42) to evaluate changes in mucosal appearance.

The PK evaluations will be based on V565 concentrations measured in serum and urine to evaluate systemic exposure (serum) and determine the levels of active V565 in urine samples.

Safety will be assessed through evaluations of AEs, clinical laboratory results, vital signs, physical examinations, ECGs and concomitant medications.

A study diagram in presented in Figure 1. The Schedule of Events is presented in .

#### Figure 1: Study Diagram

- a. Screening may be a maximum of 28 days but may be shorter depending on the amount of time required to determine that a subject is eligible for the study based on all inclusion/exclusion criteria, including laboratory values, CDAI score, CRP (or FCP) level and results of the ileocolonoscopy.
- b. All eligible subjects will have an ileocolonoscopy at Visit 2. The timing of Visit 2 is flexible, but must not occur until the subject has been declared eligible with regard to CDAI scores and CRP (or FCP) levels. The ileocolonoscopy must occur prior to Day 1.
- c. Subjects will enter an exploratory endoscopy substudy if the subject's baseline SES-CD score is ≥7 (if ileum and colon involved) or ≥4 (if the lesions are confined to the ileum).
- d. Subjects may not be randomised unless the ileocolonoscopy at Visit 2 indicates the presence of active disease.
- e. Subjects in the exploratory endoscopy substudy will have a post-treatment ileocolonoscopy scheduled for Day 42.

CDAI: Crohn's Disease Activity Index; CRP: C-reactive protein; FCP: Faecal calprotectin; R: Randomisation; SES-CD: Simple Endoscopic Score for Crohn's Disease

## 4.2 Description of Study Periods

#### 4.2.1 Screening: Visit 1 and Visit 2 (Ileocolonoscopy) (Day -28 to Day -1)

The subjects will be screened during the 28-day period prior to randomisation using the procedures outlined in to ensure that all eligibility criteria are fulfilled. Screening may be a maximum of 28 days but may be shorter depending on the amount of time required to determine that the subject is eligible for the study.

In order to have an ileocolonoscopy, eligible subjects must have sufficient diary entries to calculate a CDAI score, a CDAI score  $\geq$ 220 to  $\leq$ 450 and a CRP  $\geq$ 5 mg/L (or if CRP is normal, FCP  $\geq$ 250 µg/g) prior to Visit 2.

When it is determined that the subject is eligible for the Visit 2 ileocolonoscopy, the site will contact the subject, confirm the date and instruct the subject in the use of the preparation for the ileocolonoscopy according to local practice. All assessments scheduled for Visit 2 should be done prior to the ileocolonoscopy.

A previous ileocolonoscopy conducted within 12 weeks before Visit 1 may be substituted for the Visit 2 ileocolonoscopy provided it is forwarded to the central reader and was performed in such a way as to enable evaluation by the central reader.

Active disease must be confirmed by the central reader in order for the subject to proceed to Visit 3 and to be randomised on Day 1.

Assessments conducted at Visits 1 and 2 may be repeated once if they are out of range or unacceptable, providing that they are completed and that the results known within the screening period. The re-test value(s) will supersede the original values for the evaluation of the subject's eligibility.

If a subject cannot be declared eligible within the 28-day screening period and the Investigator wishes to re-screen the subject, the Investigator must contact the Medical Advisor for permission to re-screen. Requests for re-screening will be handled on a case-by-case basis. A re-screening can be allowed once only for an individual subject, regardless of the reason. The subject will be allocated a new screening number.

#### 4.2.2 Treatment Period

During the treatment period, the subject will attend three site visits (Day 1, Day 14 and Day 42). If possible, site visits will be scheduled for the morning. The window for the Day 14 and Day 42 visits is -3 days to +1 day.

On Day 1, subject compliance with diary completion will be reviewed to confirm that diary compliance is still acceptable. If all eligibility requirements have been met (including those based on the results of the ileocolonoscopy), the subject will be randomised. If not, the subject will be considered a screen failure and the reason for the screen fail will be recorded.

Eligible subjects will be randomly assigned to receive one of two oral regimens: V565 555 mg TID or placebo.

The Day 1 assessments and procedures presented in will be completed prior to starting treatment with study drug. Treatment will begin on Day 1 at the site and continue to Day 42. Additional information on dosing is available in Section 5.8.

Subjects will continue to fill out their diaries daily throughout the treatment period. At each visit, site personnel will review the diaries and assess compliance with study drug administration and with the use of the diary.

Pharmacokinetic samples (blood and urine) will be collected at each study visit. On Day 1, subjects will be asked to provide a pre-treatment sample and an additional sample 4 to 8 hours after the first dose of study drug.

The subjects take their last dose of study drug on Day 42. The subjects will return to the site on Day 42 for the assessments and procedures indicated in . The subject diaries will be collected at this time. Subjects participating in the endoscopy substudy will have their second ileocolonoscopy performed on Day 42.

### 4.2.3 Follow-up: Day 56

The subject will return to the site for a follow-up visit at Day 56, approximately two weeks after the last dose of study drug. The procedures performed during the follow-up visit are presented in .

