In an exploratory endoscopy substudy, subjects with more severe disease at the Visit 2 ileocolonoscopy (a SES-CD  $\geq$ 7, if ileum and colon are involved or  $\geq$ 4 if only the ileum is involved) will undergo a second ileocolonoscopy at the end of treatment (Day 42) to evaluate changes in the mucosa.

Pharmacokinetic (PK) evaluations will be based on concentrations of V565 measured in serum and urine. Safety will be assessed through evaluations of adverse events (AEs), clinical laboratory results, vital signs, physical examinations, electrocardiograms (ECGs) and concomitant medications.

Planned number of subjects:	Approximately 126 randomised to receive study drug in a
3	2:1 active:placebo ratio (84:42)
	Approximately 114 to complete (76:38) based on an estimated dropout
	rate of 10% during treatment

Diagnosis and main criteria for inclusion:	This study will enrol adult subjects with active CD. The main criteria for inclusion are:
	
 
History of CD (confirmed by ileocolonoscopy) of at least three months duration prior to Visit 1
 
CDAI score of ≥220 to ≤450 during Screening
 
CRP ≥5 mg/L (or, if CRP is normal, FCP ≥250 µg/g) at Screening
 
Active CD of ileum and/or colon as determined by the baseline ileocolonoscopy
 
Female subjects must not be pregnant and male and female subjects must agree to use effective contraception throughout the study and for 90 days after the last dose of study drug.
 
Subject must have failed or experienced intolerance to at least one of the following: aminosalicylates, corticosteroids; immunosuppressants (e.g., azathioprine [AZA], 6-mercaptopurine [6-MP], or methotrexate [MTX]).
 

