### Criteria for evaluation:

Primary Efficacy Endpoint:

 Proportion of responders at Day 42, defined as subjects achieving both CDAI ≥70-point reduction from Baseline OR CDAI score <150, AND a reduction of ≥40% from the baseline value of CRP or FCP

Secondary Efficacy Endpoints:

- Proportion of subjects achieving a ≥100-point reduction in CDAI score and a concomitant reduction of 50% in CRP or FCP at Day 42
- Proportion of subjects achieving a  $\geq$ 70-point reduction in CDAI score at Day 42
- Proportion of subjects achieving a  $\geq$ 100-point reduction in CDAI score at Day 42
- Proportion of subjects achieving a CDAI score of <150 CDAI at Day 42
- Changes from Baseline in scores for PRO-2 at Day 14 and Day 42

Safety Endpoints:

• Evaluations of AEs, clinical laboratory results, physical examination findings, ECGs and vital signs throughout the study

Pharmacokinetic Endpoint:

• Serum and urine concentration of V565 prior to first administration of study drug and at Day 14, Day 42, and Day 56. In addition, On Day 1, a post-dose urine sample will be obtained at the site 4 to 8 hours after the first dose of study drug.

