# 6.0 EFFICACY, PHARMACOKINETIC, SAFETY, HEALTH OUTCOME, AND PHARMACOGENOMIC ASSESSMENTS

### 6.1 Efficacy Assessment

### 6.1.1 Subject Diary

During Visit 1, a diary will be given to each subject. Subjects will be trained how to complete the diary and instructed in the use of the diary. The importance of completing the diary daily throughout the study will be stressed. The subject will complete the diary daily throughout the study until Day 42 (the End of Treatment Visit). The diary will be used to record the subject-reported variables of the CDAI,

Site personnel will assess the subject's compliance with the use of the diary throughout the study.

During the screening period, subjects must have entered sufficient diary data to allow calculation of the CDAI score (see Section 6.1.2). Subjects with poor compliance completing the diary during screening will be considered screen failures. Subjects with poor compliance completing the diary during the treatment period may be withdrawn from the study.

The data obtained from the subject diary will be used for calculation of the subject-reported variables of the CDAI and other efficacy outcomes measures such as the PRO-2,

The subject will record the following information in the subject diary to assess CD activity:

- 1. Number of liquid or very soft stools
- 2. Abdominal pain/cramps
- 3. General well-being
- 4. Fever over 100°F (37.8°C)
- 5. Use of anti-diarrheal drugs (e.g., loperamide, diphenoxylate, or opiates)

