### 6.1.2 Crohn's Disease Activity Index

Crohn's Disease Activity Index (CDAI) is the most commonly used measure of clinical activity in patients with CD [12, 13, 14]. Some of the data used to calculate the CDAI is obtained from the subject diary (see Section 6.1.1) and some is obtained at site visits. The CDAI will be calculated at the time points identified in .

The CDAI consists of eight variables:

- 1. Total number of liquid or very soft stools (total for previous 7 days)
- 2. Abdominal pain/cramps rating (total for previous 7 days)

- 3. Subjective general well-being rating (total for previous 7 days)
- 4. Total number of listed categories the subject has experienced during the last 7 days (Note: all of these are assessed by the Investigator with the exception of fever, which is obtained from the subject diary.)
  - a. Arthritis or arthralgias
  - b. Iritis/uveitis, erythema nodosum, or pyoderma gangrenosum
  - c. Aphthous ulcers
  - d. Anal fissures, fistulae, or abscess
  - e. Other fistula (specified by site personnel)
  - f. Fever higher than 100°F or 37.8°C during previous week
- 5. Use of anti-diarrheal drugs (e.g., loperamide, diphenoxylate, or opiates)
- 6. Presence of abdominal mass
- 7. Anaemia based on haematocrit (HCT) value entered into formula:
  - a. For men = 47 HCT value
  - b. For women = 42 HCT value
- 8. Body weight in kilograms (kg) entered into formula:
  - a. ([standard weight in kg actual weight kg] / [standard weight in kg]) x 100%

The responses are scored numerically and weighted. Total CDAI scores range from 0 to approximately 600 points; a higher score indicates a more active disease. A CDAI score of <150 points denotes remission, a score between 150 to 219 points denotes mildly active disease, a score of  $\geq$ 220 to  $\leq$ 450 points denotes moderately active disease, and a score of >450 points denotes severe disease.

During the study, the CDAI will be calculated from the scores obtained from the subject-reported variables of the CDAI and the results recorded at the site. Haematocrit values will be extracted from the central laboratory results and used for the calculation of the CDAI score.

Subjects who prematurely discontinue treatment prior to Day 42 will be asked to continue to record CDAI data until the Early Termination Visit.

Instructions for recording the CDAI score will be given at Visit 1 (see Section 6.1.1). Data should be reviewed at each study visit, including unscheduled visits.

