# 6.1.4 Abdominal Pain and Stool Frequency Instrument (PRO-2)

PRO-2 will be calculated at the time points indicated in .

The PRO-2 is a composite score that measures abdominal pain and soft stool frequency averaged over seven days [20]. The data for the total PRO-2 score is extracted from selected subject-reported variables of the CDAI included in the subject diary. These data are the entries for the number of liquid or soft stools/day and abdominal pain (rated on a scale of 0-3) assessed over the course of seven days.

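### Preparation for the Day 42 ileocolonoscopy, if taken the day before, counts in substudy subjects' Day 42 CDAI and PRO-2 but not in their screening baseline

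*Protocol*

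**What the plan says.** **Day 42.** Protocol 6.1.2 defines the CDAI stool item as "Total number of liquid or very soft stools (total for previous 7 days"), and pain and well-being use the same 7 days. Protocol 6.1.4 says: "The PRO-2 is a composite score that measures abdominal pain and soft stool frequency averaged over seven days". Both scores come from the diary, and Protocol 6.1.1 says: "The subject will complete the diary daily throughout the study until Day 42 (the End of Treatment Visit"). For subjects who qualify by SES-CD, 4.2.2 adds: "Subjects participating in the endoscopy substudy will have their second ileocolonoscopy performed on Day 42".

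**Screening.** Protocol 4.1 has the CDAI calculated before Visit 2. Note b to Figure 1 says that Visit 2 "must not occur until the subject has been declared eligible with regard to CDAI scores and CRP (or FCP) levels". An earlier ileocolonoscopy that is substituted for Visit 2 predates Visit 1, and the diary is first issued at Visit 1. SAP 6.2 makes the screening score the baseline for CDAI and PRO-2.

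**Preparation.** The only instruction is in Protocol 4.2.1, for Visit 2: the site is to "instruct the subject in the use of the preparation for the ileocolonoscopy according to local practice". No timing is given for either procedure.

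**Endpoint.** Response needs a CDAI fall of at least 70 points or a score below 150, "AND a reduction of ≥40% from the baseline value of CRP or FCP". SAP 15.1.3 analyses it by logistic regression and reports an odds ratio.

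**The concern.** At screening the protocol puts the CDAI before the procedure. At Day 42 the procedure falls on the day the diary ends, and the visible text has no matching safeguard. If preparation is taken the day before, loose stools and discomfort caused by the laxative count as Crohn's disease activity, at the end of treatment only and in substudy subjects only.

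Some subjects just past the 70-point cut-off who also meet the marker criterion would then be classed as non-responders because of an exploratory procedure. Reported response rates would be too low in both arms, and in a trial of about 126 subjects some power could be lost. Day 14 is not affected.

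**Working it through.** The plan states no figure on this point to reproduce, and the response rates behind its sample size are not visible.

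**1. Does the preparation day fall in the window?** The Day 42 visit may take place from 3 days before to 1 day after (Protocol 4.2.2), so on Days 39 to 43.
- Visit on Day 42: the previous 7 days are Days 35–41, or Days 36–42 if the visit day counts. Preparation on Day 41 is in both.
- Visit on Day 39 (preparation Day 38) or Day 43 (preparation Day 42): also inside under either reading.
- Screening: the window closes before Visit 2, so it holds no preparation day.

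**2. Size of one preparation day.** Weights from Protocol 12.1; symptom counts are assumed.

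Points = 2 × stools + 5 × pain grades + 7 × well-being grades
- 5 extra stools: 10 (14% of 70)
- 10 extra stools, one grade each of pain and well-being: 20 + 5 + 7 = 32 (46%)
- 15 extra stools, one grade each: 30 + 5 + 7 = 42 (60%)

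**3. Effect on the primary endpoint.** One CDAI cut-off is enough. Eligibility requires "CDAI score of ≥220 to ≤450 during Screening" and that score is the baseline, so a score below 150 already means a fall of more than 70.

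Composite rate = m × [(1 − f)c + f × Φ(Φ⁻¹(c) − d/SD)]

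Here c is the CDAI response rate, m the marker rate, f the share of subjects affected (0.3, 0.5, 0.7) and d the added points (10, 32, 42). The SD of CDAI change is 90. Apart from the weights behind d, these inputs are assumptions. Power is by exact binomial enumeration of the unadjusted logistic Wald test, 84 v 42 subjects, two-sided 5%.

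| c × m, placebo v V565 | Composite rates | Power without | Power with (range over f, d) | Odds ratio without | Odds ratio with |
|---|---|---|---|---|---|
| 0.375×0.40 v 0.615×0.65 | 15% v 40% | 0.841 | 0.836–0.759 | 3.77 | 3.79–3.92 |
| 0.45×0.45 v 0.643×0.70 | 20.3% v 45.0% | 0.794 | 0.789–0.720 | 3.22 | 3.21–3.25 |
| 0.50×0.50 v 0.70×0.714 | 25% v 50% | 0.779 | 0.775–0.727 | 3.00 | 2.99–3.04 |

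Mid case (second row, f = 0.5, d = 32, so d/SD = 0.356):
- Placebo: 0.45 × (0.5×0.45 + 0.5×0.315) = 17.2%
- V565: 0.70 × (0.5×0.643 + 0.5×0.504) = 40.2%
- Risk difference 24.8 to 22.9 points; odds ratio 3.22 to 3.23; power 0.794 to 0.759
- Expected responders before: 84×0.450 + 42×0.203 = 46, of whom about 5 are reclassified (1 to 10 over the grid)

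**4. How far this depends on the inputs.**
- Power loss in points over the three rows: 0.4–8.2 at SD 90, 0.3–6.1 at SD 110, 0.6–12.3 at SD 70. The largest is always at 15% v 40% with 70% affected and 42 points.
- Higher rates, SD 90: 30% v 55% loses 0.2–3.8 points; 40% v 65% runs from a 1.1-point loss to a 0.3-point gain; 60% v 85% gains 0.4–2.8.
- CDAI-only 70-point endpoint at the table's CDAI rates: from a 5.5-point loss to a 0.3-point gain.
- Type I error (equal rates of 15%, 20%, 25%; half affected, 32 points): 0.039 to 0.033, 0.045 to 0.042, 0.047 to 0.046.

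**5. PRO-2**, if it carries the CDAI weights: increment = (2 × stools + 5 × pain)/7 = 1.4, 3.6 or 5.0. The standard error of the treatment difference is multiplied by √(1 + f(1−f) × 5.0²/SD²). At f = 0.5 this is 1.02 at SD 12, 1.05 at SD 8 and 1.01 at SD 16.

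**The case against.** The strongest objection is that the deciding text may not be public. SAP 15.3.1.2 says the CDAI is calculated as defined in SAP 15.1.1, but the published 15.1.1 shows only the responder definition. The schedule of events is not shown either. A rule on which diary days count could sit in either place, and withheld text cannot be called missing. This stands as a condition. It does not change the 7-day rule visible in Protocol 6.1.2 and 6.1.4, which as written includes the preparation day.

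Second, the timing of preparation and every magnitude input except the weights are assumed. That is correct, so the results are given as ranges. Day-before preparation is plausible because 4.2.2 asks for morning visits where possible.

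Third, the harm is small. Neither arm is favoured, the odds ratio is stable, and at high response rates power rises. The power model also omits the planned covariates. All of this stands and limits the priority.

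Fourth, an earlier window moves the diary items away from the Day 42 marker sample, and the start of preparation needs a definition when local practice varies. Both are fair but minor, and the fix allows for them.

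The asymmetry also depends on the SAP baseline. Under the general definition in Protocol 8.2 (last value before first dose), a Day 1 CDAI, if one is calculated, could itself include Visit 2 preparation.

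**Conclusion.** The concern holds on its stated conditions: preparation falls on a day inside the seven, the SAP screening baseline applies, and no exclusion rule exists in the unpublished part of SAP 15.1.1. The Day 42 score of substudy subjects then carries a procedure artefact that their baseline does not.

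The effect is conservative. It lowers response rates in both arms without favouring either or raising type I error. Under the SD 90 assumptions, the power loss is 0.4 to 8.2 points at composite rates of about 15–25% v 40–50%, and it shrinks or reverses at higher rates. For PRO-2 the expected result is slightly more variance, not a biased treatment difference. The share of subjects in the substudy is not given, so the true size cannot be calculated from the documents. Priority is low to moderate; the case for acting is that the remedy is cheap.

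**What to change.** In Protocol 6.1.2 and 6.1.4 and in SAP 15.1.1, state that for subjects with a Day 42 ileocolonoscopy the Day 42 CDAI and PRO-2 diary items come from the last 7 diary days before preparation started. Define that start once for all sites and record its date in the eCRF. Report the unadjusted 7-day window as a sensitivity analysis. If SAP 15.1.1 already has such a rule, repeat it in the protocol sections so that sites collect the date.

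The cost is one derivation rule, one eCRF date and a short site instruction. The drawback is a diary window that ends one or two days earlier in substudy subjects than in the others, and correspondingly further from the Day 42 marker sample. The procedure and its preparation do not change.
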